## MODIFICATION HISTORY

Unique Identifier for this Version	Date of the Document Version	Author	Significant Changes from Previous Authorized Version
1.0	2022/12/07	[REDACTED]	Not Applicable – First version

---

Document: \\jptok-sfs02\data1\PROJ\Boehringer\NZA72277\_Biostatistics\Documentation\SAP\SAP\_text

Author: [REDACTED] Version Number: 1.0

Version Date: 07 DEC 2022

Template No.: RWI\_TP\_BIOS0013 Revision 1

Reference: RWI\_WI\_BIOS0015

Effective Date: 15Jun2018

## 1. ABBREVIATIONS

ADR	Adverse Drug Reaction
AE	Adverse Event
AESI	Adverse Event of Special Interest
ATC	Anatomical Therapeutic Chemical
BI	Boehringer Ingelheim
CI	Confidence Interval
CRO	Contract Research Organisation
EC	Ethics Committee

eCRF	Electronic Case Report Form
EDC	Electronic Data Capture
EGFR	Epidermal Growth Factor Receptor
EGFR-TKI	Epidermal Growth Factor Receptor-Tyrosine Kinase Inhibitor
eTMF	Electronic Trial Master File
HR	Hazard Ratio
ICF	Informed Consent Form
IRB	Institutional Review Board
ISF	Investigator Site File
LL3	LUX-Lung 3 study
NBI	Nippon Boehringer Ingelheim
NIS	Non-Interventional Study
NSCLC	Non-Small Cell Lung Cancer

---

Document: \\jptok-sfs02\data1\PROJ\Boehringer\NZA72277\_Biostatistics\Documentation\SAP\SAP\_text

Author: [REDACTED] Version Number: 1.0  
Version Date: 07 DEC 2022

Template No.: RWI\_TP\_BIOS0013 Revision 1

Reference: RWI\_WI\_BIOS0015

Effective Date: 15Jun2018

Statistical Analysis Plan

---

OS	Overall Survival
PD	Progressive Disease
PFS	Progression Free Survival
PS	Performance Status
SAE	Serious Adverse Event
SAP	Statistical Analysis Plan
SOP	Standard Operating Procedures
TMF	Trial Master File
TOT	Time on Treatment
TOT1	First-line TOT
TTF	Time-to-Treatment Failure
TPP	Time to Progression
UMIN	University hospital Medical Information Network

---

Document: \\jptok-sfs02\data1\PROJ\Boehringer\NZA72277\_Biostatistics\Documentation\SAP\SAP\_text

Author: [REDACTED] Version Number: 1.0

Version Date: 07 DEC 2022

Template No.: RWI\_TP\_BIOS0013 Revision 1

Reference: RWI\_WI\_BIOS0015

Effective Date: 15Jun2018

## Statistical Analysis Plan

---

### 2. INTRODUCTION

This statistical analysis plan (SAP) describes the rules and conventions to be used in the analysis and presentation. It describes the data to be summarized and analyzed, including specifications of the statistical analyses to be performed.

This SAP is based on protocol version 1.0, dated 2020/09/04 and case report forms (CRFs) ver.6.0, dated 2021/03/08.

All planned analyses identified in this SAP will be performed by [REDACTED] Real-World Evidence Solutions (RWES) Biostatistics following Database Lock.

### 3. STUDY OBJECTIVES AND OUTCOMES

The primary objective is to confirm Time on Treatment (TOT) related to afatinib treatment as the first-line therapy (TOT1) in patients with EGFR mutation-positive NSCLC. The observation in the real-world setting of the time from the start of the first-line afatinib until the end of subsequent treatment in this study will provide insights on the sequence of treatment for patients. The Japanese healthcare system will enable this study to evaluate multiple treatment options after afatinib treatment.

#### 3.1 Primary Outcome

The primary outcome of this study is TOT with afatinib in TOT1. This will be assessed as the time from the start of afatinib (Giotrif®) as first-line treatment until the end of afatinib treatment or death date by any cause, which occurs first.

---

Document: \\jptok-sfs02\data1\PROJ\Boehringer\NZA72277\_Biostatistics\Documentation\SAP\SAP\_text

Author: [REDACTED] Version Number: 1.0

Version Date: 07 DEC 2022

Template No.: RWI\_TP\_BIOS0013 Revision 1

Reference: RWI\_WI\_BIOS0015

Effective Date: 15Jun2018

Statistical Analysis Plan

---

### 3.2 Secondary Outcomes

- TOT from the start of afatinib until end of subsequent therapies in the second-line setting or death by any cause, whichever occurs first
- TOT from start of the second-line treatment until end of the second-line treatment or death by any cause (TOT2), whichever occurs first
- OS and survival rate at 18 and 36 months
- Time to initial dose reduction of afatinib
- Proportion of patients with dose modifications of afatinib

### 3.3 Safety Outcome

NA.

## 4. STUDY DESIGN

### 4.1 General Description

This study was designed as a non-interventional, multi-centre study from existing data of patients who were treated with afatinib in the first-line setting in each study site after the launch of Giotrif® on 7 May 2014 on a regular basis. In first round of data extraction, the data will be extracted retrospectively once patients are enrolled into this study. A second round of data extraction for additional follow-up will be performed one year after completion of first round data extraction.

### 4.2 Schedule of Events

The schedule of events can be found in Section 6 of the protocol.

---

Document: \\jptok-sfs02\data1\PROJ\Boehringer\NZA72277\_Biostatistics\Documentation\SAP\SAP\_text

Author: [REDACTED] Version Number: 1.0

Version Date: 07 DEC 2022

Template No.: RWI\_TP\_BIOS0013 Revision 1

Reference: RWI\_WI\_BIOS0015

Effective Date: 15Jun2018

## Statistical Analysis Plan

---

Milestone	Planned Date
Start of data extraction	Q1 2021
End of data extraction	Q3 2022
Registration in University hospital Medical Information Network (UMIN)	Register number not yet assigned as the study is not yet registered. The study will be registered shortly before the start of data extraction.
Final report of study results	Q4 2022

### 4.3 Changes to Analysis from Protocol

The following changes were made in this SAP.

- Additional subgroups will be explored in the subgroup analysis. Refer to Section 8.3 for the subgroups to be analyzed.
- All the analyses other than patient disposition and subgroup analysis by initial dose of afatinib will be repeated for patients who initiated afatinib 40mg as first-line setting.

## 5. PLANNED ANALYSES

### 5.1 Interim Analysis

The following data will be analyzed in the interim analysis.

---

Document: \\jptok-sfs02\data1\PROJ\Boehringer\NZA72277\_Biostatistics\Documentation\SAP\SAP\_text

Author: [REDACTED] Version Number: 1.0

Version Date: 07 DEC 2022

Template No.: RWI\_TP\_BIOS0013 Revision 1

Reference: RWI\_WI\_BIOS0015

Effective Date: 15Jun2018

## Statistical Analysis Plan

---

- Patient disposition (participating facilities, reasons for exclusion, etc.)
- Demographics
- Disease characteristics (stage / pathology, type of EGFR gene mutation, etc.)
- Treatment for NSCLC (first-line treatment regimen, second-line treatment regimen, treatment period, reason for treatment discontinuation)
- Outcomes described in Sections 3.1 and 3.2 other than OS and survival rate

## 5.2 Final Analysis

The following data will be analyzed in the final analysis.

- OS and survival rate described in Section 3.2.

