## 7. GENERAL CONSIDERATIONS

### 7.1 Censoring rule

Censoring rule for time-to-event outcomes is described below.

- ToT1: If patients did not discontinue first-line treatment with afatinib and did not die at the data extraction, they will be censored on the date they are last verified to have been on first-line treatment with afatinib.
- ToT: If patients did not discontinue second-line treatment and did not die at the data extraction, they will be censored on the date they are last verified to have been on second-line treatment. If patients were on first-line treatment and did not move to second-line treatment at the data extraction, ToT is same as ToT1 for these patients.
- ToT2: If patients did not discontinue second-line treatment and did not die at the data extraction, they will be censored on the date they are last verified to have been on second-line treatment.
- OS: If patients did not die at the data extraction, they will be censored on the date they are last verified to be alive.
- Time to initial dose reduction of afatinib: If patients did not reduce initial dose of afatinib at the data extraction, they will be censored on the date they are last verified to have been on the initial dose of afatinib or increased dose of afatinib.

---

Document: \\jptok-sfs02\data1\PROJ\Boehringer\NZA72277\_Biostatistics\Documentation\SAP\SAP\_text

Author: [REDACTED]

Version Number:

1.0

Version Date:

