## Statistical Analysis Plan

---

- common, uncommon [Outcomes analysed: TOT1, TOT, OS, Time to initial dose reduction of afatinib]
- each mutation type (Del19, G719X, S768I, L858R, L861Q, Exon 20 insertion, Other) [Outcomes analysed: TOT1, TOT, OS, Time to initial dose reduction of afatinib]
- T790M, Exon 20 insertion, Uncommon mutation other than T790M and Exon 20 insertion [Outcomes analysed: TOT1, TOT, OS, Time to initial dose reduction of afatinib]
  - ECOG PS at the initiation of first-line treatment (0/1, >=2) [Outcomes analysed: TOT1, TOT, OS, Time to initial dose reduction of afatinib]
  - Brain metastases at the initiation of first-line treatment (Yes, No) [Outcomes analysed: TOT1, TOT, OS, Time to initial dose reduction of afatinib]
- EGFR mutation status at the initiation of second-line treatment
  - common, uncommon [Outcomes analysed: TOT, TOT2]
  - each mutation type (Del19, G719X, S768I, L858R, L861Q, Ins 20, Other) [Outcomes analysed: TOT, TOT2]
  - T790M, Exon 20 insertion, Uncommon mutation other than T790M and Exon 20 insertion [Outcomes analysed: TOT, TOT2]
- Type of treatment class for subsequent treatment in second-line setting [Outcomes analysed: TOT, TOT2]
- Initial dose of afatinib (Patients starting afatinib 40 mg will be analysed) [Outcomes analysed: TOT1, TOT2, TOT, OS]

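### TOT1, TOT and TOT2 are scheduled for the interim analysis only, so the second extraction round appears to update nothing but survival

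*SAP*

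**What the plan says.** - SAP 3.1 makes TOT1 the primary outcome. SAP 3.2 lists TOT, TOT2, OS with survival rates at 18 and 36 months, and two dose outcomes.
- SAP 5.1 puts in the interim analysis "Outcomes described in Sections 3.1 and 3.2 other than OS and survival rate".
- SAP 5.2 has a single item for the final analysis: "OS and survival rate described in Section 3.2".
- SAP 4.1: "A second round of data extraction for additional follow-up will be performed one year after completion of first round data extraction". It does not say which data this round records.
- SAP 7.1 censors at the data extraction, in the singular, without naming a round. For patients still on first line who "did not move to second-line treatment at the data extraction, ToT is same as ToT1 for these patients".
- SAP 3 says that observing the time from "start of the first-line afatinib until the end of subsequent treatment in this study will provide insights on the sequence of treatment".
- SAP 8.3 plans TOT and TOT2 in small groups, for example "Type of treatment class for subsequent treatment in second-line setting [Outcomes analysed: TOT, TOT2".
- SAP 4.3, 13.1 and 13.2 do not say that any treatment-duration outcome is analysed again on the second round. SAP 8.1 rules out statistical tests.

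**The concern.** Follow-up is planned for a further year, but the schedule in 5.1 and 5.2 gives only OS a place to use it. If the interim analysis is run on round one and the final analysis on round two, three things follow.

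- Patients still on afatinib at round one stay censored for TOT1, and their TOT stays equal to TOT1, even if round two records when they stopped.
- Patients who start second line between the rounds never enter TOT2. They are not a random part of the cohort: most were still on afatinib at round one, so most have a long TOT1.
- A death on treatment between the rounds counts for OS but not for TOT1 or TOT, although both definitions include death.

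TOT and TOT2 carry the treatment-sequence question named in SAP 3, so the study's descriptive answer to that question would rest on the less mature data.

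**Working it through.** The SAP states no figure to reproduce: it gives no sample size, median, censoring fraction or accrual window. The check therefore has two parts.

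**Reading the schedule.** The outcomes in 3.1 and 3.2 are TOT1, TOT, TOT2, OS with survival rates, time to initial dose reduction, and proportion with dose modifications. Section 5.1 takes all of these except OS and survival rate; 5.2 takes those two. Each outcome is therefore assigned once, and none is assigned to both analyses.

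**Size of the loss, under assumed inputs.** TOT1 is exponential with median m = 15 or 20 months, and TOT2 is exponential with median 8 months. 70% go on to second line, which starts when afatinib ends; the others count as TOT events at the end of first line. Afatinib starts are uniform between a and b months before round one, with (a, b) = (12, 84) or (18, 60). N is 200. Round two adds 12 months.

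With λ = ln 2 / m, the share still on first line at round one is

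p0 = (e^(−λa) − e^(−λb)) / (λ(b − a)),

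and 12 months later p1 = p0 · e^(−12λ). The TOT2 set is 200 × 0.7 × (1 − p), so its growth is (1 − p1)/(1 − p0) − 1, in which the 70% cancels.

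For m = 20 and (18, 60): λ = 0.03466; p0 = (0.5359 − 0.1250)/1.4556 = 0.282; p1 = 0.282 × 0.660 = 0.186; growth = 0.8138/0.7177 − 1 = 13.4%.

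With λ2 = ln 2 / 8, the share still under observation for TOT at time t is

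e^(−λt) + 0.7 · λ/(λ − λ2) · (e^(−λ2·t) − e^(−λt)),

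averaged over the follow-up window at each cut.

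| m | Window | p0 | p1 | TOT2 set, N 200 | Growth | TOT censored share |
|---|---|---|---|---|---|---|
| 15 | 12–84 | 0.166 | 0.096 | 117 to 127 | 8.5% | 25% to 16% |
| 15 | 18–60 | 0.192 | 0.110 | 113 to 125 | 10.1% | 30% to 18% |
| 20 | 12–84 | 0.243 | 0.160 | 106 to 118 | 10.9% | 33% to 23% |
| 20 | 18–60 | 0.282 | 0.186 | 101 to 114 | 13.4% | 39% to 26% |

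**Precision.** The same patients were simulated at both cuts, with the Kaplan-Meier median and a log-log 95% interval from Greenwood's variance. With 12 more months:

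- the TOT2 interval is about 5 to 8% narrower;
- the TOT interval is about 2 to 5% narrower;
- the TOT1 interval is at most about 1.5% narrower, and its median shifts by at most about 0.3 month.

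As a rough check, if width goes as 1/√n, growth of 8.5 to 13.4% alone gives 1 − 1/√1.085 = 4.0% to 1 − 1/√1.134 = 6.1% for TOT2. The rest comes from longer follow-up of patients already in the set.

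On a wider grid (TOT2 median 6, 8 or 12 months; 60% or 80% of those alive going on; 10% of treatment lines ending in death), the intervals narrow by 4.5 to 9.5% for TOT2, 0.6 to 8.6% for TOT and 0 to 1.7% for TOT1.

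**Who is left out of TOT2.** In the simulation, patients who enter in the extra year have a median TOT1 of 32 to 38 months, against 15 or 20 in the whole cohort.

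**The case against.** The strongest reply is that the split may be deliberate. The protocol and case report form are not at hand, SAP 4.3 does not list the split as a change from protocol, and 4.1 speaks only of additional follow-up. If round two records survival only, no treatment data are left unused. This stands: the point is conditional on round two recording treatment data, and without that only a wording clarification remains.

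The link between interim and round one, and between final and round two, is also inferred. By the planned dates in 4.2, "End of data extraction" falls in Q3 2022, before the SAP date of 07 DEC 2022, so both rounds might already have been complete, although that table may be out of date. The inference is reasonable, but the unused year rests on it.

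It is also fair to say that Kaplan-Meier with the 7.1 censoring handles patients still on treatment, that no tests are performed, and that the gain is small. That sets the size of the point but does not remove it, because the remedy is cheap.

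Several stronger readings are tempting, and the document does not support them:

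- *The sections contradict each other.* They do not; each outcome is assigned once.
- *Everyone who enters TOT2 late has a TOT1 longer than the follow-up at round one.* This fails for patients who stopped afatinib before round one and started second line afterwards. With an assumed mean gap of 1 month, they are about 10 to 12% of late entrants.
- *The TOT2 median is materially biased.* The simulated reduction in its error, from 0.7–1.5 to 0.4–1.1 months, needs an assumed correlation of +0.3 or −0.3 between TOT1 and TOT2. With no correlation there is no such gain.
- *TOT and OS must share a cut because 8.3 lists both.* It does list them together, for example "Brain metastases at the initiation of first-line treatment (Yes, No) [Outcomes analysed: TOT1, TOT, OS, Time to initial dose reduction of afatinib", but nowhere asks for a comparison.

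**Conclusion.** The point holds as a modest, conditional improvement. The SAP plans a further year of follow-up and schedules only OS to use it, without giving a reason. On the natural but unstated reading of interim and final, what is lost is mainly precision and completeness for TOT2, less for TOT, and almost nothing for the primary TOT1 median. A reader might infer that the primary result is unreliable; the figures do not support that.

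Every magnitude rests on assumed inputs, since the SAP gives none, and on round two recording treatment data. Confidence is medium for that reason. The change is worth making because it is specific and costs little, not because the planned analysis is invalid.

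**What to change.** Amend SAP 5.2: where the second extraction records treatment data, the final analysis repeats TOT1, TOT and TOT2, with their planned subgroups (8.3) and the 40 mg repeat (6.2), on the combined data alongside OS. Label the interim results for these outcomes preliminary.

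The cost is one or two sentences and a rerun of existing Kaplan-Meier programs. The downside is that reported figures may shift slightly from the interim. No alpha is spent, because no tests are performed (8.1).

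If round two records survival only, state that in 4.1 and 5.2. That is a clarification and asks for no further chart work. Repeating the dose outcomes and showing OS at the first cut are optional and not part of this change.

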## 6. ANALYSIS SETS

### 6.1 All Subjects Enrolled [ENR] Set

The all subjects enrolled (ENR) set will contain all subjects who provide informed consent for this study. This will be used for the analysis of patient disposition.

### 6.2 Analysis Set

The analysis set will contain all enrolled subjects who fulfil all the inclusion criteria and do not present with any of the exclusion criteria. This will be used for all analyses other than patient disposition.

---

Document: \\jptok-sfs02\data1\PROJ\Boehringer\NZA72277\_Biostatistics\Documentation\SAP\SAP\_text

Author: [REDACTED] Version Number: 1.0

Version Date: 07 DEC 2022

Template No.: RWI\_TP\_BIOS0013 Revision 1

Reference: RWI\_WI\_BIOS0015

Effective Date: 15Jun2018

## Statistical Analysis Plan

---

All the analyses other than patient disposition and subgroup analysis by initial dose of afatinib will be repeated for patients who initiated afatinib 40mg as first-line setting.

## 7. GENERAL CONSIDERATIONS

### 7.1 Censoring rule

Censoring rule for time-to-event outcomes is described below.

- ToT1: If patients did not discontinue first-line treatment with afatinib and did not die at the data extraction, they will be censored on the date they are last verified to have been on first-line treatment with afatinib.
- ToT: If patients did not discontinue second-line treatment and did not die at the data extraction, they will be censored on the date they are last verified to have been on second-line treatment. If patients were on first-line treatment and did not move to second-line treatment at the data extraction, ToT is same as ToT1 for these patients.
- ToT2: If patients did not discontinue second-line treatment and did not die at the data extraction, they will be censored on the date they are last verified to have been on second-line treatment.
- OS: If patients did not die at the data extraction, they will be censored on the date they are last verified to be alive.
- Time to initial dose reduction of afatinib: If patients did not reduce initial dose of afatinib at the data extraction, they will be censored on the date they are last verified to have been on the initial dose of afatinib or increased dose of afatinib.

---

Document: \\jptok-sfs02\data1\PROJ\Boehringer\NZA72277\_Biostatistics\Documentation\SAP\SAP\_text

Author: [REDACTED]

Version Number:

1.0

Version Date:

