**13.2 Secondary outcomes**

The derivation of time-to event outcomes (TOT, TOT2, OS and time to initial dose reduction of afatinib) is described in Section 7.1.

These time-to-event outcomes will be analysed using Kaplan-Meier method, and the median along with two-sided 95% CI will be displayed (using the Greenwood’s formula for estimation of standard errors). For OS, survival rate at 18 and 36 months and its two-sided 95% CI will also be displayed.

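### Time to first dose reduction: patients who stop afatinib or die unreduced are censored, so the Kaplan-Meier median comes too early as the time by which half of patients have reduced

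*SAP*

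**What the plan says.** Section 3.2 lists "Time to initial dose reduction of afatinib" as a secondary outcome. Section 13.2 refers to section 7.1 for its derivation and gives no other rule.

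The rule in section 7.1 reads "If patients did not reduce initial dose of afatinib at the data extraction, they will be censored", and the censoring date is the date "they are last verified to have been on the initial dose of afatinib or increased dose of afatinib". Neither stopping afatinib nor death is mentioned. For TOT1 the same section is narrower: "If patients did not discontinue first-line treatment with afatinib and did not die at the data extraction, they will be censored".

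For the analysis, section 13.2 says: "These time-to-event outcomes will be analysed using Kaplan-Meier method, and the median along with two-sided 95% CI will be displayed". The outcome is carried into the section 8.3 subgroups by EGFR mutation status, ECOG PS and brain metastases, for example "Brain metastases at the initiation of first-line treatment (Yes, No) [Outcomes analysed: TOT1, TOT, OS, Time to initial dose reduction of afatinib". Under section 6.2, almost all analyses, this one included, "will be repeated for patients who initiated afatinib 40mg as first-line setting".

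**The concern.** A patient who has permanently stopped afatinib, or has died, cannot have a later dose reduction. Kaplan-Meier censoring treats that patient as still able to reduce, at the same rate as those who remain on drug. The resulting median belongs to a hypothetical setting in which nobody stops or dies first. The SAP does not say that this is the quantity it wants, and in a description of real-world treatment most readers will take the median as the time by which half of the patients had reduced.

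The median with its confidence interval is the only summary that section 13.2 specifies for this outcome. In the subgroups, groups with the same reduction hazard but different stopping rates would show the same median although different shares of their patients ever reduce.

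**Working it through.** **1. Who is censored.** The section 7.1 rule applies to anyone without a reduction at data extraction. A patient who stopped for good or died on the starting or an increased dose meets that condition. The last date verified on that dose is then about the end of afatinib. No other rule in the SAP covers this patient.

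**2. Direction.** Let a(t) be the hazard of reduction and b(t) the hazard of stopping or death without reduction.
- One minus Kaplan-Meier estimates 1 − exp(−∫a).
- The share of patients who have actually reduced by t is the cumulative incidence, ∫a(u)·exp(−∫₀ᵘ(a+b))du.

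The second integrand carries the extra factor exp(−∫b) ≤ 1, so one minus Kaplan-Meier is never below the cumulative incidence. It lies above it as soon as someone leaves before a later reduction. This holds for any rates.

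**3. Size.** The SAP gives no reduction or stopping rate and no expected median for this outcome, so there is no stated figure to reproduce and all rates below are assumptions. With constant monthly hazards a and b:
- Kaplan-Meier median = ln2 / a
- share ever reducing = a/(a+b)
- share reduced by the Kaplan-Meier median m = a/(a+b) × (1 − exp(−(a+b)m))
- time to 50% = −ln(1 − 0.5(a+b)/a)/(a+b), not reached if a ≤ b

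Example, a = 0.10 and b = 0.05:
- m = 0.693/0.10 = 6.9 months
- share reduced by then = 0.667 × (1 − exp(−0.15 × 6.93)) = 0.667 × (1 − 0.354) = 43%
- time to 50% = −ln(0.25)/0.15 = 1.386/0.15 = 9.2 months

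| a / b per month | Kaplan-Meier median (months) | Time to 50% actually reduced (months) | Actually reduced by the Kaplan-Meier median |
|---|---|---|---|
| 0.231 / 0.01 | 3.00 | 3.06 | 49% |
| 0.231 / 0.03 | 3.0 | 3.2 | 48% |
| 0.15 / 0.05 | 4.6 | 5.5 | 45% |
| 0.10 / 0.05 | 6.9 | 9.2 | 43% |
| 0.05 / 0.05 | 13.9 | never reached | 37.5% |

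A case where fewer than half ever reduce: with a = ln2/12 and b = ln2/10, the share is (1/12)/(1/12 + 1/10) = 45%, yet Kaplan-Meier reports a median of 12 months.

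**4. Reductions concentrated early.** The reduction hazard changes at 3 months and the stopping hazard is 0.03 to 0.05 (numerical integration):
- 0.25 then 0.03: Kaplan-Meier median 2.8 months, time to 50% 2.9 to 3.5 months
- 0.20 then 0.03: Kaplan-Meier median 6.1 months, time to 50% 8.1 to 10.2 months

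**5. Simulation check.** For 200,000 patients with a = ln2/6 and b = ln2/15, the Kaplan-Meier median was 5.96 months, 44.3% had reduced by then, and the time to 50% was 7.40 months. The formulas give 6.0 months, 44.4% and 7.44 months.

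**6. Subgroups.** Take two groups with a = 0.10 and with b = 0.03 and 0.08. The Kaplan-Meier median is 6.9 months in both, but half have actually reduced at 8.1 and 12.8 months.

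**The case against.** The strongest reply is that the SAP never says the median is meant as the time by which half of all starters have reduced. Censoring at the end of afatinib and applying Kaplan-Meier gives a recognised on-treatment tolerability summary, and the protocol, which was not available for this check, may define the outcome that way. On that view the fault is a missing label, not a wrong estimator. This stands in part: the early bias exists only relative to the descriptive reading. But the SAP does not state the on-treatment reading. That reading also needs stopping to be independent of reducing, which is doubtful where intolerance leads some patients to reduce and others to stop.

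The contrast with TOT1 shows no inconsistency, because discontinuation and death are TOT1 events by definition. That is fair. The contrast shows only that the dose-reduction rule leaves stopping and death unmentioned; that they are censored follows from the rule covering everyone without a reduction.

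Output templates might show curves or event counts, and section 3.2 also plans a proportion with dose modifications. The proportion gives some protection against the worst misreading, but it has no time axis and is not specific to reductions.

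The stakes are modest. The outcome is secondary, section 8.1 excludes statistical tests, section 8.3 allows subgroup analyses to be changed or dropped, and the size rests on assumed rates that can make it negligible. All of this stands, and it limits the weight of the point without removing it.

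**Conclusion.** The concern holds. Read as the time by which half of patients have reduced, the planned median is never late and generally early, whatever the rates. The size cannot be fixed from the SAP. Over the assumed hazards it runs from negligible (3.00 against 3.06 months), when reductions come early relative to stopping, to a reported 13.9 months when 50% is never reached. Sizes other than the early-peaking cases assume constant hazards.

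This is a worthwhile improvement to a secondary descriptive outcome, not a threat to the study's main result. TOT1, TOT, TOT2, OS and the proportion with dose modifications are unaffected.

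**What to change.** In sections 7.1 and 13.2:
- Estimate the cumulative incidence of first dose reduction with the Aalen-Johansen estimator, taking permanent afatinib discontinuation and death before reduction as competing events.
- Censor only patients still on afatinib without a reduction, at their last verification.
- Report the incidence with 95% CI at fixed times chosen in advance, and the time to 50% if it is reached.
- Apply the same to the section 8.3 subgroups that use this outcome and to the 40 mg repeat analysis.
- If the Kaplan-Meier median is kept alongside, label it as a hypothetical on-treatment quantity.

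The cost is a change of wording and a little more analysis work. No new data are needed, because TOT1 already requires stop and death dates. The one drawback is that the time to 50% may have to be reported as not reached.
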